- **Side hop test (SHT):** subjects will be asked to jump laterally and medially between two tape marks 30 cm apart 10 times as fast as possible. One repetition is considered a lateral jump of 30 cm and return to the starting position. Two sets shall be performed and the total time in seconds required to complete each set shall be recorded. The time shall be recorded by a hand held stopwatch to the nearest hundredth of a second (ICC 0.84, SEM 2.10 seconds and MDC 5.82 seconds). The rest between sets will be one minute and the lowest time will be used for the study. If a participant falls, puts the contralateral foot on the ground or does not correctly complete the 30 cm distance between lines we consider this as invalid and the participant should repeat the test again. (51)

- **Countermovement jump unilateral test (CMJ Unilateral):** for this test, subjects will be asked to jump vertically in a standing position with their hands placed on their pelvis. Firstly, there will be a descent phase in which the subjects will bend the knee approximately 90 degrees and then take off as quickly as possible, keeping the lower limb extended during the flight phase. The limb that we do not assess will be kept off the ground at all times. Three repetitions will be performed with a rest of 30 seconds between each one, where we will keep the highest value. The My Jump 2 application installed on an iphone® 11 running iOS 15.1 (Apple Inc., USA) will be used for the measurement. The validity of the application has been found to be high (ICC= 0.997, 95% (Intraclass Coefficient (ICC): 0.996-0.998, P < 0.001) with an almost perfect correlation coefficient (r= 0.995, P< 0.001) between the application and the gold standard, which is a strength platform. Finally, in the reliability analysis, the data are also high (ICC = 0.999, 95% CI= 0.998-0.999, P < 0.001) with an inter-observer difference of 0.1 ± 0.4 cm (52,53).

-Measurement of isometric ankle strength of three muscle groups: invertors, eversors/plantarflexors, invertors/dorsiflexors. Isometric assessment of the ankle in inversion/dorsiflexion and eversion/plantarflexion selectively assesses the tibialis anterior and peroneus longus and peroneus brevis muscles respectively.

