- **Numeric Pain Rating Scale (NPRS):** scale used for the assessment of pain intensity, where 0 is no pain and 10 represents maximum pain. (59) There are no data for the MCID in patients with CAI, however, it seems that changes between 1.5 and 2.1 points can be considered as the MCID

for patients with musculoskeletal pain conditions. (60,61). This variable will ask about pain intensity during sports practice.

-Range of Motion (ROM): The range of motion of dorsal ankle flexion will be measured with the My Rom application (version 3.0.4) installed on an iPhone 11 running iOS 15.1 (Apple Inc., USA). Its validity with respect to the Limit® mini digital inclinometer ($r = 0.989$, 95% CI = 0.986-0.993) and reliability (ICC = 0.976, 95%CI = 0.966- 0.983, Dorsiflex app: (Coefficient of variation) CV = $5.1 \pm 2.3\%$; Digital inclinometer: 185 CV = $4.9 \pm 2.5\%$) has been demonstrated during the loaded lunge test (62).

To measure the dorsiflexion angle, subjects must be placed in a lunge or knight in burden position with the knee flexed and the foot resting on the ground. The device is then placed just below the tibial tuberosity (touching the screen to the subjects' tibia), aligning the z-axis of the phone with the tibia, and then clicking GO on the device screen. Finally, the application will start a 5-second countdown and at the end will record the angle of inclination on the X-axis of the iphone. Three measurements will be taken with a one minute break between measurements.

Before the initial assessment measurements were taken, the subjects completed a 5-minute warm-up of treadmill walking at a self-selected pace plus mobility and muscle activation exercises lasting 3 minutes.

The investigator in charge of the assessments will first examine the pain scale, secondly range of motion, thirdly strength, fourthly balance and lastly function, first with objective tests and finally with self-report tests.

3. Randomisation:

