All patients will be asked to report any type of adverse event they may experience throughout the study and up to one month after completion. An adverse event is defined as a sequela of average duration with any symptom perceived as painful or unacceptable by the participant and requiring treatment (67). As needle insertion in some patients may induce post-treatment discomfort, subjects will be advised to report any incidences. EPMN has adverse effects that are infrequent and not serious, such as post-puncture pain that usually lasts from a few hours to a few days of mild intensity, the possible appearance of a haematoma that will be minimised thanks to the use of ultrasound and pressure techniques on the area, nerve irritation that will be minimised as much as possible by the use of ultrasound again and finally the possibility of infection, so a disinfectant will be used on the area before the technique and single-use gloves. The therapeutic exercise programme has subsequently been used by other research groups and is very safe because it is an incremental programme adapted in intensity individually to each

subject. Possible adverse effects are also rare, where the most common may be increased ankle pain, which will be controlled by adapting the load, the possible generation of delayed onset muscle soreness, which usually has a peak duration of 48 hours and a possible fall with instability and disturbance work, which is minimised by the presence of the therapist monitoring the session at all times.

Sample size calculation:

The sample size and power calculation was calculated with the software G-Power 3.1.9.4 (Heinrich Heine Universität Düsseldorf) (68). Calculations were based on the detection of an 8-point mean difference (MCID) on each FAAM scale (46), assuming a standard deviation of 6.5, a 2-tailed test, an Alpha level of 0.05 and a desired power of 90%. The estimated sample size is 15 participants per group.

Statistical analysis of data:

1. Descriptive data in mean, range and standard deviation.
2. Normal distribution/homoskedasticity of the data (See whether the data are parametric or non-parametric). Kolmogorov-Smirnov test and Levene's test.
3. Comparison of means between two groups (experimental group and placebo control group) using Student's t-test to analyse the differences between the quantitative dependent variables of the study. If the data are non-parametric, we will use the Wilcoxon statistic.

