4. Calculate the effect size of the difference between pre and post on the different variables with the cohen's d calculation. A effect size less than 0.2 will be considered trivial, between 0.2-0.5 low, between 0.5-0.8 moderate and greater than 0.8 high.

Data management:

The data will be managed in the following way:

1. Data capture: data will be collected through the data collection notebook which will be obtained by the researcher in charge of the assessments.
2. Classification and storage: each patient will be assigned a control number, in order to maintain the anonymity of the patient over the principal investigator to avoid possible biases. This number will be recorded in a database (Access Sheet) where all patients will be listed in order to identify them in the successive taking of values. This database will

be kept during the execution of the research, and will only be used at the time of data collection, and only the principal investigator of the study will have access to it. Each patient will be identified by this control number and by a code formed by the initials of their first name and their first surname. The data will be stored on the principal investigator's personal computer, access to which is only possible with a username and password available to the same person.

3. Use and treatment: The use is exclusively scientific, without any kind of profit motive. Once the data have been coded, they will be entered into the SPSS statistical package for the corresponding statistical calculation, which will be carried out by the researcher in charge of the analysis. In the dissemination of the results there will be absolute confidentiality of the participant's personal data.
4. Assignment and transfer of data to a third party for processing: No data will be transferred to a third party for processing.
5. Destruction: the data in the collection notebook will be destroyed by a paper shredding machine and the data in the database will be kept for a maximum period of 10 years, after which it will be completely deleted from the researcher's personal computer.

Ethical considerations:

All participants will receive information on the main aspects of the study and will be asked to complete an informed consent form in accordance with applicable law. The procedures to be carried out in this study will follow the ethical standards of the Declaration of Helsinki.

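### Item 4 grades a bare point estimate of Cohen's d, with no confidence interval and no link to the item 3 test, so at 15 per group the verbal label is mostly noise

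*Combined protocol and SAP*

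**What the plan says.** Under 'Statistical analysis of data', item 4 reads "Calculate the effect size of the difference between pre and post on the different variables with the cohen's d calculation", followed by the grading rule "A effect size less than 0.2 will be considered trivial, between 0.2-0.5 low, between 0.5-0.8 moderate and greater than 0.8 high".

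Item 4 does not say whether d is taken within each arm or between arms, which SD is the standardiser, or whether the sign counts. It gives no confidence interval. The only confidence intervals in the document belong to cited validity and reliability figures in section 2.2.

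Item 3 separately compares the two groups, "using Student's t-test to analyse the differences between the quantitative dependent variables of the study", with a Wilcoxon test as the non-parametric alternative. Nothing connects its result to the grade in item 4.

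The sample size section states "The estimated sample size is 15 participants per group".

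**The concern.** A grade based on a point estimate is informative only if the estimate is precise relative to the width of the bands. The low and moderate bands are each 0.3 wide. With 15 per group, the standard error of a between-arm d is larger than that, so sampling error alone can move a result across one or more bands.

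Two consequences follow. Outcomes with no true effect will often be described as showing a low or moderate effect. And since the plan does not relate the grade to the test, a report could state both that the groups do not differ significantly and that the effect is moderate, for the same outcome, with no guidance on how to read the two together.

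**Working it through.** **Inputs.** From 'Sample size calculation': "Calculations were based on the detection of an 8-point mean difference (MCID) on each FAAM scale", and "assuming a standard deviation of 6.5, a 2-tailed test, an Alpha level of 0.05 and a desired power of 90" per cent; 15 per group. From item 4: cut-offs 0.2, 0.5 and 0.8. The pre-post correlation r is not in the documents and is an assumption, ranged from 0 to 0.9.

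**The plan's own figure.** The standardised difference is 8/6.5 = 1.23. The two-sample t-test (noncentral t, two-sided 0.05) has power 0.880 at 14 per group and 0.902 at 15. The stated 15 per group reproduces.

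**Between-arm d, true value zero.** With n = 15 per arm, d = t × √(2/15) on 28 df, so the null standard error is √(2/15) = 0.365 and the approximate 95% half-width is 1.96 × 0.365 = 0.72. Grading the absolute value:

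- low or better: P(|t₂₈| > 0.2/0.365 = 0.548) = 0.588
- moderate or better: P(|t₂₈| > 0.5/0.365 = 1.369) = 0.182
- high: P(|t₂₈| > 0.8/0.365 = 2.191) = 0.037

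If only results favouring the experimental arm count, the first figure halves to 0.294.

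**Within-arm d, change over the SD of change.** Here d = t/√15 on 14 df. With no true change over time, P(|t₁₄| > 0.2 × √15 = 0.775) = 0.451 for low or better, 0.073 for moderate or better and 0.008 for high.

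**Within-arm d on the averaged raw SD.** Simulation of 200,000 trials with no true change, graded low or better by absolute value:

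| Assumed r | 0 | 0.5 | 0.7 | 0.8 | 0.9 |
|---|---|---|---|---|---|
| Probability | 0.59 | 0.44 | 0.33 | 0.24 | 0.10 |

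**When the true effect sits mid-band.** For a between-arm d, a true 0.65 is graded moderate 31% of the time. An observed 0.65 has an exact 95% interval of -0.09 to 1.38, which spans all four grades. For the within-arm d over the SD of change, a true 0.65 is graded moderate 39% of the time, and an observed 0.65 has an interval of 0.08 to 1.20, which also reaches all four grades.

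**Against item 3.** The two-sided 5% critical value on 28 df is 2.048. A t-test on the same contrast is therefore significant only if |d| > 2.048 × 0.365 = 0.748. All of the low band and the moderate band up to 0.748 are non-significant under item 3.

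**Small-sample bias.** The Hedges factor on 28 df is 1 - 3/(4 × 28 - 1) = 0.973. Applying it moves 0.588 to 0.578.

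**The case against.** The strongest reply is that nothing is decided by the grade. Item 3 tests the groups, and no sentence says that a label supports a claim. That is correct and limits the point: the missing allowance for sampling error concerns the label, not the test. It does not remove the conflict, because the two will be reported side by side and the plan does not say how to read them together.

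A reader might infer that 59% is simply the error rate of item 4. The documents do not support that. Item 4 names a pre-post difference, and 59% needs a between-arm contrast, a matching standardiser and grading by absolute value, none of which is stated. Under the within-arm reading the null is also a different one: both arms receive supervised exercise, so no change over time is neither likely nor the trial's question.

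A reader might also infer that the grades are all the plan offers on effect size. They are not. Item 1 gives means and SDs, item 3 compares means, and section 2 quotes MCIDs for FAAM, CAIT and NPRS and minimum detectable changes for the side hop test and SEBT.

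Read literally, the trivial band takes in every negative d. That matters because the pain scale improves downward ("where 0 is no pain and 10 represents maximum pain") and so does the side hop test ("the lowest time will be used for the study"), while FAAM and CAIT improve upward. Such bands are ordinarily applied to magnitude, so this needs a statement of direction and no more. Small-sample bias is a lesser matter still.

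**Conclusion.** The point holds as a modest one. Item 4 labels a point estimate without showing its precision, and at 15 per group the label is mostly noise.

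For a true zero, the chance of low or better is about 59% (between-arm, absolute value), 29% (between-arm, favourable direction only), 45% (within-arm change over the SD of change), or about 59% down to 10% on the raw SD as r rises from 0 to 0.9. It is small only when the raw SD is used and r is very high. These figures assume normal data and 15 analysed per group. The documents state no dropout rate, and fewer completers would make the grade noisier.

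The conflict with item 3 below |d| = 0.748 applies when d is between-arm, uses the same contrast as item 3, and the t-test rather than the Wilcoxon test is used. The sample size and the item 3 test are unaffected. This is a cheap improvement to reporting, not a fault in the design.

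**What to change.** In item 4:

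- Compute the standardised effect size for the between-group difference in change from baseline, and name the standardiser.
- Orient every outcome so that a positive value favours the experimental group.
- Report the effect size with its 95% confidence interval. Hedges' g may replace d, but this is optional, since it changes the value by only about 3%.
- Show the interval beside any verbal grade, and state that no conclusion about the presence or size of an effect will be drawn from the grade alone.

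Allowing a grade only when the interval excludes zero would not be a good substitute. It would require |d| above 0.748, or g above 0.748 × 0.973 = 0.728. *Low* could then never be awarded, and *moderate* would be assigned only about 7% of the time at a true d of 0.65. That repeats item 3 and mixes significance with size.

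The cost is one extra calculation per outcome and less favourable wording for some outcomes. Design and sample size do not change.
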